7.3. Vital Signs

Descriptive statistics for vital signs (e.g., systolic and diastolic blood pressure, respiratory rate, temperature and pulse rate) and their changes from baseline at each post-baseline visit will be presented by treatment group and overall.

Vital sign values will be considered PCS if they meet both the observed value criteria and the change from baseline criteria listed in Table 4. The number and percentage of subjects with PCS baseline and/or post-baseline values will be tabulated by treatment group and overall. The percentages will be calculated relative to the number of subjects with values for each vital sign parameter in each treatment group at the analysis visit. The numerator is the total number of subjects with at least 1 PCS vital sign value at the analysis visit. A supportive listing of subjects with post-baseline PCS values will be provided including the subject number, site, baseline, and post-baseline PCS values.

Table 4: Criteria for Potentially Clinically Significant Vital Signs

Vital Sign Parameter	Flag	Criteria ^a	
		Observed Value	Change from Baseline
Systolic blood pressure (mmHg)	High	≥180	Increase of ≥20
	Low	≤90	Decrease of ≥20
Diastolic blood pressure (mmHg)	High	≥105	Increase of ≥15
	Low	≤50	Decrease of ≥15
Pulse rate (beats per minute)	High	≥120	Increase of ≥15
	Low	≤50	Decrease of ≥15

^a A post-baseline value is considered as a PCS value if its meets both criteria for observed value and change from baseline.

All vital signs data will be listed for the safety set.

7.4. Physical Examination Findings

Any relevant findings from the baseline physical examination are to be reported on the medical history. Any relevant findings from the post-baseline physical examination are to be reported as AE's. No separate physical examination findings were collected to summarize.

7.5. Complete Ophthalmic Exam

Results of the ocular assessments will be summarized by shift tables showing the shift from baseline in the individual slit-lamp examination and indirect ophthalmoscopy endpoint. These will be provided by treatment group, overall and visit for study eye and fellow eye. The visits to be presented are Month 12, Month 24, and LOV.

Any relevant findings from the post-baseline ophthalmic examination are to be reported as AEs.

The change from baseline in chronic (first measurement of the day) IOP will be summarized over time by treatment group. In addition, the incidence of IOP above specified thresholds (i.e., >21 mmHg at pre-injection/chronic (first measurement of the day); >30 mmHg post injection) will be summarized by treatment group and overall, protocol specified timepoint (at Month 12 and Month 24 readout, respectively) and over the whole study.

The mean change from baseline in the chronic IOP \pm the standard error will be plotted over time by treatment group.

Details of the ocular assessments will be provided in listings for the safety set and for IOP, the ITT set.

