## 4.2. Risk/Benefit

The Phase I (Study POT-CP043014; NCT02461771) and Phase 2 (Study POT-CP121614; NCT02503332) studies provide supporting evidence of a positive benefit-risk profile for the use of pegcetacoplan in treating patients with AMD, specifically patients with GA. These preliminary results of an up to 28% reduction of GA progression rate support the evaluation of pegcetacoplan in a Phase 3 study.

The reported safety data from these studies demonstrated an acceptable safety and tolerability profile with no clinically significant safety concerns observed. A total of 178 patients have received at least 1 dose (15 mg/injection) of pegcetacoplan as part of these studies. In the Phase 2 study in patients with GA an imbalance in new exudation in subjects treated with pegcetacoplan was observed. [Section 4.1.4](#) provides a summary of the study design and key results from both studies.

The safety monitoring practices employed by this protocol (complete ophthalmologic exam, IOP monitoring, optical coherence tomography (OCT), fluorescein angiography (FA), vital signs, hematology, serum chemistry, urinalysis, physical exam, vital signs, and AE questioning) are adequate to protect the subjects' safety. There are also risks associated with the ophthalmic procedures required for participants in this study. However, these are all standard procedures that are widely performed in ophthalmology.

In the days following any IVT injection, patients are at risk of developing sterile or infectious intraocular inflammation (eg, endophthalmitis). In recent studies conducted with pegcetacoplan IVT from a single manufacturer, events of transient moderate and severe intraocular inflammation have been observed. Other risks of IVT injection include traumatic cataract, retinal detachment, increased IOP, and hemorrhage.

The amount of blood (see [Section 9.16](#)) planned for collection from each subject over the 24 months of the study does not pose an undue risk in this patient population.

There is a potential health benefit for trial participants from receipt of study drug. If efficacious, pegcetacoplan is expected to alter the course of GA and slow its rate of progression.

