**Table 1: Treatment Arms With Approximate Number of Subjects**

Treatment arms
Pegcetacoplan 15 mg/0.1 mL monthly for 24 months (n = approximately 200 subjects; 24 pegcetacoplan injections)
Pegcetacoplan 15 mg/0.1 mL every other month for 24 months (n = approximately 200 subjects; 12 pegcetacoplan injections)
Sham monthly for 24 months (n = approximately 100 subjects; 24 sham injections)
Sham every other month for 24 months (n = approximately 100 subjects; 12 sham injections)

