## 8. STUDY PROCEDURES

A study schema is presented below in [Figure 1](#). All randomized subjects will return every month to the clinical site for assessments and additional pegcetacoplan or sham injections according to their randomization scheme until Month 12. From Month 12 onwards, subjects will return to the clinical site based on their randomized treatment schedule (monthly or EOM) and will follow the treatment regimen and assessments outlined in the Visit Schedule until Month 24. In addition, subjects will be contacted via phone by masked study staff 4 ( $\pm 2$ ) days after the first 3 study treatments to collect safety information.

The end of this trial for each subject is defined as when the subject completes their Month 24 study visit, approximately 30 days (monthly treatment group) and approximately 60 days (EOM treatment group) after the last visit at which IP is administered. The period following last dose of IP is sufficient to evaluate the safety of pegcetacoplan based on its half-life in the vitreous; further details can be found in the pegcetacoplan IB. At the end of the 24-month study period, subjects will be offered entry to enroll into a separate open-label study.

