## APPENDIX A: VISIT SCHEDULE—Monthly Group—Screening, Day 1 Through Month 12 (Continued)

Abbreviations: AH50 = alternative pathway of complement functional test; BCVA = best corrected visual acuity; CH50 = classical pathway of complement functional test; CNV = choroidal neovascularization; DCFP = digital color fundus photography; eCRF = electronic case report form; FAF = fundus autofluorescence; FFA = fundus fluorescein angiography; FRI = Functional Reading Independence Index; IOP = intraocular pressure; LL-BCVA = low luminance best corrected visual acuity; MNREAD = Minnesota Low-Vision Reading Test; NEI VFG-25 = National Eye Institute Visual Functioning Questionnaire 25-Item Version; NIR = near infrared reflectance; OCT-A = optical coherence tomography angiography; PK = pharmacokinetics; SD-OCT = spectral domain optical coherence tomography; SE = study eye; Term = termination; VEGF = vascular endothelial growth factor.

Note: All ocular assessments are to be performed for both eyes unless annotated with 'SE' (study eye) in the above schedule. All assessments should be performed on the same day.

All study visits should be scheduled and projected based on the Day 1 visit date with the exception of Visit 2a which should be based on the Day 1 dose date.

- A. For subjects that discontinue the study early, the early termination assessments should be performed after a minimum of 30 days have passed from the last dosing visit. If a subject reports for a scheduled visit and decides to terminate early prior to dosing, the visit should be considered the early termination visit and all early termination procedures should be performed. At Month 24, all subjects should be offered entry into an open-label study.
- B. At Day 1 (Visit 2), confirm subject eligibility through reviewing the inclusion/exclusion criteria and receive confirmation of eligibility from the reading center.
- C. Significant medical/surgical history from the previous 5 years. Anti-VEGF treatments (fellow eye) and invasive ocular procedures performed within the past 5 years and while on study should also be recorded. Any history of tobacco use should be recorded.
- D. Obtain prior to fluorescein angiography and before study drug administration.
- E. At screening, serum pregnancy should be performed for women of childbearing potential. If positive, subject is not eligible to continue in the study.

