2.2.5. Safety Endpoints

- Incidence and severity of ocular and systemic treatment-emergent adverse events.
- Incidence of ADA directed against pegcetacoplan peptide or PEG.
- Incidence of new active CNV in the study eye.
- Incidence of new onset of subclinical CNV in the study eye.
- Incidence of subjects who lost letters based on NL-BCVA categories (≥ 15 , $\geq 15 - < 30$, ≥ 30 ETDRS letters).
- Change/shift from baseline in clinical labs and incidence of abnormal lab values.
- Change from baseline in vital signs and incidence of abnormal vital sign results.
- Shift from baseline in ocular examination assessments including slit-lamp examination and indirect ophthalmoscopy.
- Change from baseline in Intra Ocular Pressure (IOP) and incidence of IOP above specified thresholds.
- Change/shift from baseline in ocular imaging assessments (including specular microscopy; select sites).

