7. SAFETY ANALYSES

Safety analyses will be performed using the Safety set. Safety variables include adverse events (AEs), deaths, clinical laboratory results, vital signs, incidence of ADA against pegcetacoplan, ocular assessments (e.g., NL-BCVA, IOP and ophthalmic examinations), and ocular imaging.

At the time of the Month 12 reporting, safety summaries will be produced based on the complete Month 12 data. At the time of the final study reporting, safety summaries will be produced based on cumulative data.

For each safety variable, the last value collected before the first dose of investigational product will be used as baseline for all analyses of that safety variable. Last Observed Value (LOV) will be defined as the last valid assessment obtained after baseline. The LOV will be presented for the Month 12 reporting as well as the final study reporting.

All safety analyses will be conducted according to the actual treatment the subject received. Unless otherwise specified, all safety summaries will be performed on the Safety set.

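### The graded eye-examination shift tables stop at Month 12, Month 24 and last observed value, so transient post-injection inflammation gets no whole-study comparison of grades between arms

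*SAP*

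**What the plan says.** SAP 2.2.5 includes among the safety endpoints "Shift from baseline in ocular examination assessments including slit-lamp examination and indirect ophthalmoscopy". SAP 7.5 plans shift tables for each slit-lamp and ophthalmoscopy item, by arm and by eye, and then restricts them: "The visits to be presented are Month 12, Month 24, and LOV". SAP 7 defines the third of these: "Last Observed Value (LOV) will be defined as the last valid assessment obtained after baseline". Under SAP 13.4, by-visit summaries use an unscheduled or early-termination result only when the scheduled one is missing.

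Protocol 4.2 gives the timing of the risk, "In the days following any IVT injection, patients are at risk of developing sterile or infectious intraocular inflammation", and its nature: in recent studies with product from a single manufacturer, "events of transient moderate and severe intraocular inflammation have been observed".

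Protocol 8 places the Month 24 visit "approximately 30 days (monthly treatment group) and approximately 60 days (EOM treatment group) after the last visit at which IP is administered". For subjects who leave early, footnote A to Appendix A says "the early termination assessments should be performed after a minimum of 30 days have passed from the last dosing visit", unless the subject decides to stop at a scheduled visit before dosing.

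Protocol 9.13 requires anterior-chamber cells and flare to be graded on the Appendix H scales and vitreous cells on the Appendix I scale. It also refers to Appendix I for vitreous haemorrhage density, but the printed Appendix I grades vitreous cells only.

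**The concern.** The documents describe a reaction that starts within days of an injection and then resolves. The shift tables look at the eye at about the point furthest from an injection: just before the next dose at Month 12, and one full dosing interval after the last dose at Month 24. LOV adds little. For a completer it repeats a tabulated visit, and for an early leaver it is normally an examination at least 30 days after dosing. The examinations best placed to catch a reaction are unscheduled ones. Protocol 8.1.6 requires all safety assessments when a subject returns because of an adverse event, yet those results normally do not enter the tables.

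At stake is how this endpoint will be read. The shift tables could look much the same in the pegcetacoplan and sham arms whether or not graded inflammation came and went between the tabulated visits.

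The SAP treats comparable data differently. SAP 7.5 itself summarises the incidence of raised intraocular pressure over the whole study. SAP 7.6 and 7.7 show letter loss, fundus haemorrhage, subretinal fluid and cystoid spaces at each visit. SAP 13.6 uses every post-baseline assessment to identify potentially clinically significant values.

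**Working it through.** **Inputs.** Visit days are 30 × month, with the first dose on Day 1 (Protocol Appendices A to D). Protocol Table 1 gives "24 pegcetacoplan injections" in the monthly arm and 12 in the EOM arm. With no Month 24 injection (Protocol 8.1.4.2), doses fall at Months 0 to 23 (monthly) and Months 0, 2, …, 22 (EOM). Visit windows are ±8 days for monthly, and for EOM ±8 days in year 1 and ±16 in year 2 (Protocol Appendix K). The documents give no duration for an inflammatory episode, so a range is assumed. The Month 12 slit-lamp examination is taken to precede the Month 12 dose. The protocol says this for images; for the slit lamp it is inferred from the order of the schedule.

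**1. The stated interval reproduces.**
- Month 24: monthly 720 − 690 = 30 days; EOM 720 − 660 = 60 days.
- Month 12: monthly 360 − 330 = 30 days; EOM 360 − 300 = 60 days.

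**2. With visit windows.** Both the dose and the examination can move.
- Monthly: 30 ± 16 = 14 to 46 days.
- EOM at Month 12: 60 ± 16 = 44 to 76 days.
- EOM at Month 24: 60 ± 32 = 28 to 92 days.

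The temporary COVID-19 dosing windows can shorten the minimum further: 30 − 15 − 8 = 7 days (monthly), 60 − 30 − 8 = 22 (EOM, Month 12) and 60 − 30 − 16 = 14 (EOM, Month 24).

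**3. Share of scheduled examinations used.** Scheduled post-baseline slit-lamp examinations number 12 + 12 = 24 (monthly) and 12 + 6 = 18 (EOM). For a completer the tables use 2/24 = 8.3% and 2/18 = 11.1%.

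**4. What the tables can catch.** For each nominal injection, suppose a finding persists for L days from the dose. Count the injections for which a tabulated visit, or any scheduled visit, falls within those L days.

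| L (days, assumed) | Monthly, tabulated | EOM, tabulated | Monthly, any scheduled | EOM, any scheduled |
|---|---|---|---|---|
| 7, 14 or 28 | 0% | 0% | 0% | 0% |
| 30 | 2/24 = 8.3% | 0% | 100% | 6/12 = 50% |
| 45 | 2/24 = 8.3% | 0% | 100% | 6/12 = 50% |
| 60 | 4/24 = 16.7% | 2/12 = 16.7% | 100% | 100% |
| 90 | 6/24 = 25% | 2/12 = 16.7% | 100% | 100% |

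The first scheduled examination after a dose is at 29 or 30 days (60 days for EOM in year 2). Tabulating every scheduled visit would therefore help only for findings lasting about a month or more. Shorter findings can be captured only through unscheduled examinations.

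**The case against.** The strongest reply is that shift tables at fixed visits describe lasting change, and that transient events belong in the adverse-event analysis, which is well provided for. SAP 7.5 sends relevant post-baseline examination findings into the adverse-event data and lists the examination details. SAP 7.1 tabulates treatment-emergent endophthalmitis and intraocular inflammation by preferred term for each eye and per injection for the study eye, along with summaries by maximum severity, seriousness and relationship. Protocol 7.5.3 makes every endophthalmitis case a serious event. A data monitoring committee sees unmasked data about every 6 months (SAP 12).

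This stands, and it defeats a stronger reading. A reader might infer that the inflammation will hardly appear in the safety report at all. The documents do not support that: it is nearly absent from the graded shift tables, not from the report. Nor is 30 to 60 days a fixed bound. It is nominal timing, and LOV can come from an unscheduled examination closer to a dose.

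It is also fair that short episodes would enter a worst-grade table mainly through unscheduled examinations, many of which will already be adverse events. The table would add the grade more often than it adds a new case.

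What the reply does not supply is the grade itself, compared between arms. Adverse-event entry depends on the investigator judging a finding relevant. Severity in Protocol 11.3.2 is a general scale built on intervention and daily activities, not the Appendix H and I grades. Listings compare nothing.

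**Conclusion.** The point holds as a gap in reporting, not as a hidden safety signal. The shift tables for a listed safety endpoint normally use 2 of 24 (monthly) or 2 of 18 (EOM) scheduled examinations, nominally 30 or 60 days after a dose. They will show almost none of the short-lived inflammation that Protocol 4.2 describes: 0% of injections for findings of 7 to 28 days in either regimen, and 0% up to 45 days for EOM. No other planned output compares the cell and flare grades between arms over the whole study.

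The percentages assume onset at the dose, nominal visit timing, the durations shown and a slit-lamp examination before dosing at Month 12. Visit windows would let some shorter findings through, particularly in the monthly arms, where the gap can be as short as 14 days. The efficacy conclusions are unaffected. This is a cheap improvement worth making.

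**What to change.** Add to SAP 7.5, for each eye and arm, a shift table from baseline to the worst post-baseline grade of aqueous cells, flare and vitreous cells. Include vitreous haemorrhage on whatever scale was actually collected, since none is printed in Appendix I. Use all scheduled, unscheduled and early-termination examinations, and state that the SAP 13.4 rule on unscheduled results does not apply to this table. Produce it for the first 12 months and for 24 months, and keep the existing tables.

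The cost is a few extra tables from data already collected, with no change to study procedures. A worst-grade summary favours arms examined less often, and EOM subjects have 6 fewer scheduled examinations in year 2. The 12-month table is therefore the cleaner comparison across regimens. Even there, the COVID-19 minimum schedule lets EOM subjects skip visits without dosing, so report the number of examinations per subject beside the table.

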7.6. NL-BCVA

The number and percentage of subjects who lost letters compared with baseline at each visit based on NL-BCVA in the study and fellow eye will be presented. The three categories are ≥ 15 , $\geq 15 - < 30$ and ≥ 30 ETDRS letters.

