#### **8.1.4.2. Months 13-24**

##### **8.1.4.2.1. Visits 15-26 (Monthly Group) and 15-20 (Every-Other-Month Group)**

During this phase, clinic visits will follow treatment designation (ie, the monthly subjects will return monthly for dosing and assessments and the EOM subjects will return EOM for dosing and assessments). At select sites, subjects will complete the home-based digital assessments weekly during this period.

A complete ophthalmic exam including slitlamp exam of the cornea, iris, anterior chamber, lens, and aqueous reaction (cells and flare), dilated fundus exam of the vitreous and retina, and IOP measurement will be performed and imaging collected per the Visit Schedule.

Blood should be drawn for safety labs, PK, and complement profile (select sites), anti-pegcetacoplan antibodies, and genotyping, prior to the administration of fluorescein as per the Visit Schedule. Samples will be collected for the clinical repository for those subjects that consented to this portion.

Prior to dilating the eyes, all functional tests should be performed (NL-BCVA, LL-BCVA, and MNREAD or Radner Reading Charts [in select countries]). The quality of life measures (NEI VFQ-25 and FRI) should be administered by the masked site staff.

Images should be performed including FAF, FFA, SD-OCT, OCT-A (select sites), endothelial cell count (select sites), and NIR and sent to the reading center for evaluation per the visit schedule.

IVT (or sham) injection should be performed by the unmasked physician as described in the MOP (noting no injections at Month 24) and the study eye should be monitored post injection as outlined in [Section 9.15](#).

In the event that a subject is early terminated from the study, all early termination procedures should be performed even if they are outside the allowed study window.

If the subject would like to discontinue dosing but is amenable to continuing in the study, the site should make every effort to have the subject complete as many follow-up visits as possible.

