4. STATISTICAL ANALYSIS SETS

Two sham treatment arms (SM and SEOM) will be pooled into a single control (Sham) group for analyses.

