4.4. Safety Set

The Safety set consists of all subjects randomized who receive at least one injection of pegcetacoplan or sham. Subjects will be analyzed according to the actual treatment received. In the case a subject received an incorrect injection of study medication than what they were randomized to, subjects will be presented under the corresponding pegcetacoplan arm if they received at least one injection of pegcetacoplan during the study and will only be presented under the corresponding sham arm if they did not receive any injections of pegcetacoplan. This population will be used for all safety analyses.

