6.3.2.3. NL-BCVA Score

The mean NL-BCVA score for the study eye will be summarized and analyzed in a similar fashion as the primary efficacy endpoint using MMRM described in Section 6.2.2. The model will include treatment (PM, PEOM, Sham), presence of CNV in the fellow eye (yes or no), and baseline GA lesion area ($< 7.5 \text{ mm}^2$ or $\geq 7.5 \text{ mm}^2$) as fixed effects; baseline NL-BCVA score as a covariate, time (in months) as a factor; the time \times treatment interaction term as well as the baseline NL-BCVA score \times time interaction term. Note, for the second year, only timepoints that were measured for all three treatment groups will be included in the model.

The observed values for the NL-BCVA will be summarized by treatment group and visit for both the study and the fellow eye. Summaries will present the descriptive statistics for baseline, absolute values and change from baseline data.

The mean change from baseline in the NL-BCVA score for the study eye \pm the standard error as well as the LS mean of the change from baseline in the NL-BCVA score for the study eye \pm the standard error will be plotted over time by treatment group.

In addition, the categorical changes (improvements of ≥ 15 , ≥ 10 to < 15 , ≥ 5 to < 10 , and minimal/no change (-4 to 4), worsening of ≥ 5 to < 10 , and ≥ 10 to < 15 and ≥ 15) for the study eye will be summarized by treatment group and visit.

The shift from baseline in the NL-BCVA of the study eye categories (≥ 70 , $\geq 60 - < 70$, $\geq 35 - < 60$, $\geq 20 - < 35$, < 20 ETDRS letters over time will be presented by treatment group and visit. The above-mentioned ETDRS letter thresholds are based on WHO definitions for vision impairment and blindness. WHO criteria were implemented in an attempt to capture the progressive nature of

Geographic Atrophy and the ultimate treatment goal of avoiding successive vision impairment and blindness through application of active treatment (Pegcetacoplan vs. Sham).^[1]

The average NL-BCVA score over the last 3 months for each reporting period (Month 10 - Month 12 for the Month 12 reporting; Month 22 - Month 24 for the Month 24 reporting) will be calculated for each subject who has at least one NL-BCVA assessment in these windows. The observed values for the NL-BCVA and changes from baseline will be summarized by treatment group for the study eye. Summaries will present the descriptive statistics for baseline, absolute values and change from baseline data.

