7.2. Clinical Laboratory Data

All laboratory parameters collected at each center's local laboratory will be normalized by converting values in original units to values in SI units and classified as normal, low, or high based on normal ranges supplied by the local laboratories and upon employing standardization.

Observed and change from baseline clinical laboratory data (hematology, chemistry and urinalysis) will be summarized by treatment group and protocol specified time points for the following clinical laboratory variables.

Hematology	Hemoglobin, hematocrit, red blood cells (RBC), platelet count, white blood cell count (WBC)– total and differential.
Biochemistry	Aspartate transaminase, alanine transaminase, alkaline phosphatase, sodium, potassium, chloride, bicarbonate, blood urea nitrogen (BUN), bilirubin (total, direct and indirect), creatinine, creatine kinase, glucose, and albumin.
Urinalysis	Glucose, specific gravity, blood, ketones, protein, bilirubin, pH, urobilinogen, leukocyte esterase, and nitrite.

Clinical laboratory test values are potentially clinically significant (PCS) if they meet either the low or high PCS criteria listed in [Table 3](#). The number and percentage of subjects with baseline and/or post-baseline PCS values will be tabulated by treatment group and overall.

The percentages will be calculated relative to the number of subjects with available values for

each lab parameter in each treatment group at the analysis visit. The numerator is the total number of subjects with at least 1 PCS value at the analysis visit. A supportive listing of subjects with post-baseline PCS values will be provided including the subject number, site, baseline, and post-baseline values.

Table 3: Criteria for Potentially Clinically Significant Laboratory Tests

Parameter	SI Unit	Lower Limit	Higher Limit
Biochemistry			
Albumin	g/L	<25 g/L	
Alanine Aminotransferase (ALT)	U/L		≥3*ULN
Alkaline Phosphatase (ALP)	U/L		≥3*ULN
Aspartate Aminotransferase (AST)	U/L		≥3*ULN
Bilirubin, Direct	umol/L		>1.5*ULN
Bilirubin, Total	umol/L		>1.5*ULN
Bicarbonate	mmol/L	<LLN	
Blood Urea nitrogen	mmol/L		>2.5*ULN
Chloride	mmol/L	<90 mmol/L	>115mmol/L
Creatinine	umol/L		≥178.8 umol/L
Creatine kinases	U/L		≥3*ULN
Glucose	mmol/L	<3.05 mmol/L	≥8.88 mmol/L
Potassium	mmol/L	<3.5 mmol/L	>5.5 mmol/L
Sodium	mmol/L	<130 mmol/L	>150 mmol/L
Hematology			
Hemoglobin	g/L	<0.9*LLN	
Hematocrit	%	<0.9*LLN	
Platelet Count	10 ⁹ /L	<LLN	
Urinalysis			

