13. DATA HANDLING CONVENTIONS

13.1. General Data Reporting Conventions

Continuous variables will be summarized using the number of non-missing observations (n), mean, SD, median, quartile 1, quartile 3, minimum, and maximum. Geometric mean and CV will be included for PK parameters, where appropriate. Categorical variables will be summarized using frequencies and percentages. Unless stated otherwise, for all percentages, the number of subjects in the analysis population for the treatment group will be the denominator.

Unless otherwise specified, the estimated mean and median for a set of values should be printed out to 1 more decimal place than the original values, and standard deviations should be printed out to 2 more decimal places than the original values. The minimum and maximum should report the same number of decimal places as the original values. Percentages will be displayed with 1 decimal place; except percentages will not be presented when the count is zero and 100% will be presented as an integer.

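### Read literally, the SAP's default denominator halves the pooled-sham percentage for letter loss at the six odd-month visits of the second year

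*SAP*

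**What the plan says.** SAP 7.6 covers three categories of letter loss (15 or more, 15 to under 30, and 30 or more) and requires "The number and percentage of subjects who lost letters compared with baseline at each visit based on NL-BCVA in the study and fellow eye". It gives no denominator and does not restrict the visits.

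Four other provisions decide what that table will contain:

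- **Denominator.** SAP 13.1: "Unless stated otherwise, for all percentages, the number of subjects in the analysis population for the treatment group will be the denominator". The same section withholds the percentage when the count is zero.
- **Population.** SAP 7: "Unless otherwise specified, all safety summaries will be performed on the Safety set". SAP 4.4: "The Safety set consists of all subjects randomized who receive at least one injection of pegcetacoplan or sham".
- **Columns.** SAP 4: "Two sham treatment arms (SM and SEOM) will be pooled into a single control (Sham) group for analyses".
- **Schedule.** Protocol 8.1.4.2.1, for Months 13 to 24: "the monthly subjects will return monthly for dosing and assessments and the EOM subjects will return EOM for dosing and assessments". The visual-acuity row for the EOM groups in protocol Appendix D and SAP Table 11 is marked at Months 14, 16, 18, 20, 22 and 24 only.

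Elsewhere the SAP deals with both parts of the problem. For the NL-BCVA model, 6.3.2.3 says "Note, for the second year, only timepoints that were measured for all three treatment groups will be included in the model", and 6.4.1 does the same for LL-BCVA. For laboratory data, 7.2 departs from the default denominator ("The percentages will be calculated relative to the number of subjects with available values for" the parameter at that visit), and 7.3 does likewise for vital signs. Section 7.6 contains neither provision.

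**The concern.** A by-visit percentage is meaningful only if the people in the denominator could have been counted in the numerator. At the odd months of the second year, half of the pooled Sham group and all of the pegcetacoplan EOM group have no scheduled acuity test. Under the default denominator, absence of a visit becomes absence of vision loss.

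Letter loss is a listed safety endpoint (SAP 2.2.5) for a drug injected into the eye. The artefact runs in two directions. Monthly pegcetacoplan would look about twice as bad as sham, and EOM pegcetacoplan would appear to have no losses at all. The Sham series would also alternate between odd and even months purely because of the visit calendar.

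**Working it through.** **Inputs**

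- Planned size about 600, allocated 2:2:1:1 (SAP 3.4). Protocol Table 1 gives arms of about 200, 200, 100 and 100.
- Pooling, population and denominator: SAP 4, 4.4, 7 and 13.1.
- Visits: protocol 8.1.4.2.1 and Appendix D; SAP Table 11.
- True rate of letter loss, p: not in the documents. I assume it is equal in all arms and show 5%, 10% and 15%.

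**Step 1. Reproduce the planned arm sizes.** 600 × 2/6 = 200 for monthly pegcetacoplan (PM) and 200 for EOM pegcetacoplan (PEOM). 600 × 1/6 = 100 for monthly sham (SM) and 100 for EOM sham (SEOM). These match protocol Table 1. Pooled Sham = 100 + 100 = 200.

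**Step 2. Find the affected visits.** The odd months after Month 12 are 13, 15, 17, 19, 21 and 23, which is 6 of the 12 second-year visits. Unscheduled visits cannot fill them for EOM subjects, because SAP Table 6 has no odd-month window after Month 12. For example, Day 390 (Month 13) falls in the 376 to 450 window and is assigned to Month 14. Section 7.6 has no carry-forward rule.

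**Step 3. Apply the default denominator at an odd month, with no dropout.**

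- PM = 200p / 200 = p
- Sham = (100p + 0) / 200 = p/2
- PEOM = 0 of 200, so a count of 0 with the percentage withheld under 13.1

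| Assumed p | PM shown | Sham shown | PEOM shown | Sham at an even month |
|---|---|---|---|---|
| 5% | 5% | 2.5% | 0, no percentage | 5% |
| 10% | 10% | 5% | 0, no percentage | 10% |
| 15% | 15% | 7.5% | 0, no percentage | 15% |

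The last column is 200p / 200 = p.

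**Step 4. Allow for dropout.** If a fraction d is missing equally in every arm, PM = (1 − d)p and Sham = (1 − d)p/2. With p = 10%, d = 10% gives 9% against 4.5%, and d = 30% gives 7% against 3.5%. The ratio stays at 2. Equal dropout lowers all arms at every visit but adds no bias between them.

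**Step 5. Apply the corrected denominator.** With subjects assessed at the visit as the denominator, odd-month Sham = 100p / 100 = p, which equals PM.

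**Step 6. See where else the default reaches.** The by-visit categorical changes in 6.3.2.3 (NL-BCVA) and 6.4.1 (LL-BCVA), and the NL-BCVA shift table in 6.3.2.3, fall under the same rule on the mITT set. The SD-OCT shift tables in 7.7 fall under it on the Safety set. In each, unless the shell carries a missing category, the pooled Sham categories would add up to about 100/200 = 50% at an odd month.

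**The case against.** The best counter-argument is that 7.6 never says all treated subjects form the denominator. That follows from a general convention, and the two nearby safety sections that discuss by-visit percentages both use subjects with values. The table shells, which are not in the documents, may already do so here. This is a fair reason to say *read literally* rather than to state the result as certain. It does not remove the point. Sections 7.2 and 7.3 show that the SAP states an exception when it wants one, and 7.6 states none.

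It is also true that a careful reader has clues. The continuous NL-BCVA summary in 6.3.2.3 must report the number of non-missing observations, so the drop at odd months would show there. Section 7 also calls for a last-observed-value presentation. If that is applied to letter loss, it is immune to the visit calendar. These clues limit the damage but do not correct the percentages in 7.6, which shows only the losers and so has no row revealing the missing half.

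Some stronger readings are tempting, but the documents do not support them:

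- **PEOM would be reported as 0%.** It would not, because 13.1 withholds percentages for zero counts. A bare 0 can still be misread.
- **The same flaw affects an LL-BCVA shift table.** Section 6.4.1 has categorical changes but no shift table.
- **The odd-month rows must be dropped.** With the right denominator, odd-month PM against Sham is in effect PM against SM, which is a legitimate randomised comparison. Removing the rows would discard half of the second-year visits for about 300 monthly subjects (200 + 100).

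**Conclusion.** The point holds as a defect in a stated rule, not merely as missing detail. Taken as written, SAP 7.6 with 13.1 shows the pooled Sham rate of letter loss at half its true value at six of the twelve second-year visits, while PM is shown at its true rate and PEOM as an unexplained zero.

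The factor of one half rests on the planned 1:1 split of SM and SEOM. In general it is SM / (SM + SEOM), so actual arm sizes would move it slightly. The rates of 5% to 15% only illustrate it; the ratio of 2 does not depend on them when the true rate and dropout are equal across arms.

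A reader might infer that the trial's conclusions are at risk. They are not: these tables are descriptive, with no test or decision rule attached. Month 12 and the even months including Month 24 are free of the schedule artefact, and the NL-BCVA and LL-BCVA models already use common visits only. The change should be made, because this is an ocular safety table and the correction is simple.

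**What to change.** Add to SAP 7.6 that, at each visit, the denominator is the number of subjects with a baseline and a non-missing NL-BCVA value at that visit. Show that number in the table. Mark the PEOM column as not assessed at odd months after Month 12.

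Apply the same rule to the by-visit categorical changes in 6.3.2.3 and 6.4.1, the NL-BCVA shift table in 6.3.2.3 and the SD-OCT shift tables in 7.7. This is in line with the available-value denominators in 7.2 and 7.3, although those sections do not mention a baseline value; a change from baseline needs one.

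The odd-month rows can stay. Limiting second-year rows to visits scheduled for all arms, as the acuity models do, is an optional alternative. The cost is SAP wording and table shells; no data collection changes.
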